
**TEMPLATE: RESEARCH PROTOCOL**

NUMBER	ACTIVE DATE	PAGE
HRP-503	02-04-2020	16 of 35

encryption of data (i.e., encryption “at rest”) on its database server. (This is not to be confused with encryption of data “in transit” (i.e., via SSL) to the database, which should always be done.) The encryption of database data is not necessary if the database server is properly secured. All documents that are uploaded and/or stored in REDCap will be stored on the local REDCap web server in a secure directory. To help protect and secure the data stored in Redcap’s back-end database, the software application employs various methods to protect against malicious users who may attempt to identify and exploit any security vulnerabilities in the system. Such methods will be described here in technical detail:

In REDCap, all incoming data gets intentionally filtered, sanitized, and escaped. This includes all data submitted in an HTTP Post request and all query string data found in every URL when users access REDCap, among other modes through which user-defined data gets submitted in the application. Server environment variables that are vulnerable to forgery by end-users are also checked and sanitized. All user-submitted data is properly filtered for any possibly harmful markup tags (e.g., <script>) and is then escaped before ever being displayed on a web page within the application. SQL queries sent to the database server from REDCap are all properly escaped before being sent. If any values used in an SQL query originated from user-defined values, they would also have already been sanitized beforehand, as described above. User-defined data used within SQL queries have their data type-checked to prevent any mismatching of data types (e.g., making sure a number is really a number). These processes of sanitization, filtering, data type checking, and escaping all help to protect against methods of attack, such as Cross-Site Scripting (XSS) and SQL Injection. To specifically protect against Cross-Site Request Forgery (CSRF), which is another method of attack, REDCap utilizes a “nonce” (a secret, user-specific token) on every web form used in the application. The nonce is generated as a unique value for each new HTTP request in every REDCap session.

Additionally, REDCap employs “rate-limiting” on its web pages, in which there is a set maximum number of web requests per minute that are allowed from a single IP address, and after that maximum is hit, the IP address of that user is permanently banned from REDCap. The rate-limiting value of requests per minute per IP is customizable and can be modified within Redcap’s Control Center. Rate limiting prevents denial of service attacks by bots as well as preventing other types of hacker attacks that require making many requests to the server in a short amount of time, such as with a BREACH attack. Regarding the prevention of BREACH attacks specifically, in addition to using rate limiting, REDCap always outputs an invisible string of random text of random length on every web page (to conceal the page’s true length) as an effective technique for mitigating such an attack. Redcap’s use of a unique nonce token on every web form also greatly diminishes the possibility of a BREACH attack.

## TEMPLATE: RESEARCH PROTOCOL

NUMBER	ACTIVE DATE	PAGE
HRP-503	02-04-2020	17 of 35

About the security of cookies used by REDCap, all session cookies and other cookies related to authentication that are created by REDCap will automatically have the “HTTP Only” attribute set to TRUE. By default, the “Secure” cookie flag will be set to FALSE. while this is slightly more insecure, setting its value as TRUE can sometimes cause login issues with certain server configurations, such as reverse proxies. So, for compatibility reasons, it is set as FALSE by default. However, CCHMC administrators can enable the “Secure” flag of session cookies to improve security by setting session.cookie\_secure=On in the REDCap web server’s PHP.INI configuration file.

### Administrative controls

University of Cincinnati Medical Center Division of Oral and Maxillofacial Surgery Research Coordinator, [name], has complete administrative control over the individuals involved with the research project. Any research members involved must formally apply to University of Cincinnati Health Office of Clinical Research. This application entails a confidentiality and data security agreement which must be signed and approved, which holds the employee liable for violating HIPAA policies and patient confidentiality. Otherwise, the process of gaining access to the UC charting systems is rigorous and extensive, including drug screening, badge identification application, IT registration, etc. The research member has an orientation overseen by the Research Coordinator, to adjust them to the project, including the rules and regulation of maintaining patient confidentiality. CITI training is required of all participants, including annual confidentiality agreements.

On REDCap, the Research Coordinator is given full rights to everything within the project, after which they may grant other users access to the project and limit those users' privileges as desired. Within each project, there are user controls to limit access to various functionality and modules, such as being able to export data, to enter data, to add or modify database fields or survey questions, to build or run reports, to modify user privileges, to view the logging records, and so on.

### **17.3 Describe any procedures that will be used for quality control of data collection.**

REDCap has a built-in audit trail that automatically logs all user activity and logs all pages viewed by every user, including contextual information (e.g., the project or record being accessed). Whether the activity be entering data, exporting data, modifying a field, running a report, or add/modifying a user, among a plethora of other activities, REDCap logs all actions. The logging record can itself be viewed within a project by users that have been given privileges to view the Logging page. The Logging page allows such users to view or export the entire audit trail for that project, and to filter the audit trail in various ways based upon the type of activity and/or user. The built-in audit trail in REDCap allows administrators to be able to determine all the activity and all the data viewed or modified by any given user. This structural aspect

**TEMPLATE: RESEARCH PROTOCOL**

NUMBER	ACTIVE DATE	PAGE
HRP-503	02-04-2020	18 of 35

	
of REDCap allows for close monitoring of data from the study supervisors. Additionally, only the research coordinator will have capability to add or remove data. REDCap allows the coordinator to designate or prevent specific rights to be assigned from team members.
 
17.4 Describe how data or specimens will be handled study wide as outlined below.
 
17.5 What information will be included in the data or associated with the specimens?
 
No specimens will be collected. The information collected will be as follows:
 
 
Procedural Time
 
Cost differential via model utilization
 
3D Printing Likert scale Questions answered by specialist post operatively
 

--	---

	
17.6 Who will have access to the data or specimens?
 
No specimens will be collected. Data access will be restricted to the research coordinator, the principal investigator, and co-investigators
 
17.7 Where and how data or specimens will be stored?
 
No specimens will be collected. As discussed earlier, all the data will be stored on REDCap.
 
17.8 How long the data or specimens will be stored?
 
No specimens will be collected. The data will be stored for the duration of the study, which is expected to take approximately two years, and for the duration of data analysis and peer-reviewed publication, which is expected to take another year. Realistically, the data will be stored for three years.
 
17.9 If applicable, how data or specimens will be transported?
 
Not Applicable.
 
17.10 Who is responsible for receipt or transmission of the data or specimens?
 
Not Applicable.

--	--

18.0 PROVISIONS TO MONITOR THE DATA TO ENSURE THE SAFETY OF SUBJECTS	
18.1 For more than minimal risk research, describe the plan to periodically evaluate the data collected regarding both harms and benefits to determine whether the subjects remain safe.
 
The participants will be undergoing surgical repair at UCMC for a mandible fracture. The participants participation in the study only lasts for the duration of the procedure. The evaluation of the data will be assessed following the completion of the procedure by the surgeon consented for participation in answering the Likert Scale questions. Routine surgical monitoring associated with current standards of care will be conducted by the surgical staff in the procedure room as assigned on the patients care team.
 
18.2 What data are reviewed, including safety data, untoward events, and efficacy data?

---	---

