**1.2 Describe the hypotheses to be tested.**

The investigators will test the hypothesis that patients randomized to the intervention (3D printing with pre-bent plate) arm have less operative room time and less time for the critical part of the procedure than patients in the control arm (no 3D printing, current standards of care). Personalized medicine and care for fracture treatment.

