**4.1 Detail the investigators' experience as it pertains to the study.**

**4.0 INVESTIGATOR EXPERIENCE**

[name] has been a member of the UC Surgery faculty since 2008. He is currently associate professor of surgery and is serving as the chief of OMS at UC Medical Center and Cincinnati Children's Hospital. [name] obtained his dental degree from Bangalore University, India, and trained in Oral and Maxillofacial Surgery at Emory University's College of Medicine in Atlanta, Georgia. Upon completion of residency, [name] pursued further fellowship training in Oral & Maxillofacial Surgery focusing on orthognathic surgery at Dalhousie University, Halifax, Canada. He currently serves on the Committee of Education and Training (CET) of the AAOMS and is the chair of the special committee on Emerging leaders in OMS. He is also a consultant to the AAOMS Committee on Anesthesia (CAN) on Simulation in Anesthesia. [name] was in the first class of single degree oral and maxillofacial surgeons that were recognized as Fellows of the American College of Surgeons.

[name] is Vice Chair of Operations & Quality at the University of Cincinnati Department of Radiology, and he is the clinical lead for the 3D printing section at UCH. He is the past-Chair of the American College of Radiology Appropriateness Criteria, and the Founding Chair of the Radiological Society of North America 3D Printing Special Interest Group. He also is currently the Editor-in-Chief of the journal 3D Printing in Medicine. [name] obtained his medical

	
degree through the physician scientist program at Harvard -MIT (Medicine and Medical Engineering), and he completed his residency in Diagnostic Radiology at the Brigham and Women's Hospital and Harvard Medical School, Boston, MA.

5.0 STUDY ENDPOINTS	
	
5.1 Describe any primary and secondary study endpoints.
 
Outcome 1: Noninferiority of the clinical outcome (defined by OMS on the post-op, follow up exam approx. 6 weeks out) Based on physical exam
 
Outcome 2:
 
 
Total time in the OR
 
Time in the OR considered critical part of the procedure by the OMS Staff
 
 
Outcome 3
 
 
Subjective outcome to surgeon Likert scale
 
 
5.2 Describe any primary and secondary safety endpoints.
 
Not Applicable.

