	
6.1 Thoroughly describe the study design.
 
We plan to conduct a randomized controlled trial on trauma patients brought to either UCMC or UC HH OMS for treatment of isolated mandibular fractures. This study plans to elucidate whether the utilization of 3D models during operations where effective in minimizing both OR time and operational costs. Subjects will be identified based off the initial physical assessments made by surgical specialists from OMS, Plastic Surgery, and otolaryngology. Once the subjects are identified the research coordinator will conduct a screening of the patient to ensure they meet the inclusion/ exclusion criteria for the study and then randomize the patient into either normal standard of care for surgical repair of the fractured mandible or normal standard of care for surgical repair of the fractured mandible aided by a 3D printed model of the patient's jaw. Any chart reviewing will be conducted from existing electronic medical records maintained by UC Health EPIC and OMS Vision. All the following data would be based on the patient's condition at the time of surgery.

	
Following completion of the procedure, for the surgeons who received aide via the 3D model they will be asked to answer a brief Likert Scale survey outlining their thoughts how effectively or ineffectively the model assisted them. In addition to this information, if they feel the model increased efficiency saving time, they will be asked to state how much time they felt was saved. This time differential will be compared to current CPT codes for OR time to understand how much in operational costs were saved by utilizing the models.

6.0 PROCEDURES INVOLVED	

6.2 Detail the procedures being performed, specifically the interaction or intervention with human subjects and/or their identifiable information. Please be clear and concise and provide information relevant to the current study. For
	

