**6.3 Describe procedures being performed to monitor subjects for safety or minimize risks.**

Several steps are taken to assure patient safety for surgical procedures. Prior to the procedure, their vitals are taken, including their blood pressure, heart rate, respiratory rate, and oxygen saturation. Depending on the patient, especially those with history of cardiopulmonary disease, monitors are kept cycling every five minutes during the procedure. A thorough history and physical is performed before any procedure to assure appropriate patient selection and to rule out more emergent issues. During the procedure, patients are continuously monitored with active physical examinations by the provider. There is always a certified oral and maxillofacial assistant with the patient in the room, especially during the procedure. For urgent-add on, a registered nurse is normally present as well to monitor the patient. The patient is treated via standard protocol of the oral and maxillofacial clinic at Holmes Hospital, which treats thousands of patients annually through safe, effective, and efficient measures. As explained earlier, emergency crash carts, including rescue airway carts, are present at the facility, as well as dozens of trained personnel promptly available if needed.

**6.5 Where applicable, list and describe the data collection tools such as surveys, data collection forms, etc. All tools described should be uploaded in the RAP Smart Form on the Local Site Documents page unless they are standardized, validated tools.**

Data collection will only be stored and collected on REDCap, which is a server software maintained by Cincinnati Children's Hospital Medical Center (CCHMC) informational technology team. The surgeon assigned to the case will fill out the questionnaire outlining the how effective using the 3D model was during the procedure. The outcome data will then be collected on the same secured software.

**6.6 Describe all data that will be accessed and collected during the study and how that data will be obtained (how it will be accessed).**

Description – Distinguish between data accessed and data collected if applicable.

	6.7 If there is a long-term follow-up plan (once all research related procedures are completed), what data will be collected during this period.
	No Long-Term Follow-Up

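### Two operating times are to be compared between arms, but the data list names one undefined time, and nothing fixes when the critical part starts and ends in either arm

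*Protocol*

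**What the plan says.** Section 1.2 predicts that patients in the 3D-printing arm will "have less operative room time and less time for the critical part of the procedure than patients in the control arm". Section 5.1 repeats the two times as separate items under Outcome 2: "Total time in the OR" and "Time in the OR considered critical part of the procedure by the OMS Staff". Neither section limits the second time to one arm.

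Section 17.5 introduces its list with "No specimens will be collected. The information collected will be as follows". Three items follow: "Procedural Time", a cost differential, and the surgeon's Likert answers. Section 6.6 asks what data will be collected and how, and contains only the form's own prompt.

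The one data collection tool described in section 6.5 is a surgeon questionnaire: "The surgeon assigned to the case will fill out the questionnaire outlining the how effective using the 3D model was during the procedure". Section 6.1 limits it to one arm: "for the surgeons who received aide via the 3D model they will be asked to answer a brief Likert Scale survey". Its question on time is also subjective. If surgeons think the model helped, "they will be asked to state how much time they felt was saved".

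**The concern.** By the protocol's own rationale (sections 1.1 and 2.3), the gain comes from shaping plates on the model before surgery instead of by hand in theatre. Critical-part time lies closest to that mechanism. Total room time also contains everything else that happens in the room. So the time most likely to show an effect is the one with the weakest provision for measurement.

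Two things could go wrong if the text is followed as it stands. A form built from 17.5 could carry a single procedural interval, and the critical-part time would not be recorded. Or it is recorded, but each case's boundaries are set by staff opinion, possibly after the event, by people who know the arm and expect a saving. Section 18.7 already states that no patient will spend longer in the operating room.

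A statistical analysis plan cannot repair either problem. It can say how a duration is analysed, but it cannot supply clock times that nobody took.

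**Working it through.** The protocol gives no figure on this point to reproduce, so the check sets its sections side by side.

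**What is needed**
- Two durations per procedure (1.2 and 5.1).
- Section 11.1 plans 50 + 50 = 100 procedures, so 2 × 100 = 200 durations.

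**What each section provides**

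| Section | Total OR time | Critical-part time |
|---|---|---|
| 5.1 endpoints | named | named; judged by OMS staff; no start, end, recorder or source |
| 6.1 chart review (EPIC, OMS Vision) | source plausible, variable not named | nothing says a chart holds it |
| 6.1 and 6.5 surgeon survey | no | no; perceived saving only, 3D arm only |
| 6.6 data and how obtained | template prompt | template prompt |
| 17.1 analysis | no | no; Likert scoring only |
| 17.5 data list | one undefined time item | the same single item |

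Total OR time has clear events in principle (into and out of the room) and a plausible source in routine records. Critical-part time has neither. The gap is the same in both arms, because the survey in the 3D arm does not ask for a duration of the critical part.

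**Why judgement matters here.** Let Δ be the true difference in critical-part time. Let b3D and bC be the average shift, in minutes, that staff judgement adds in the 3D and control arms. The expected observed difference is

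Δ + (b3D − bC).

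A shift common to both arms cancels; one that depends on the arm does not, and no sample size removes it. The protocol gives no basis for a value of b3D − bC, so none is assumed. Three features of the protocol make a non-zero value possible:

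1. The surgeon who uses the model knows the arm. Section 3.4 calls the study blinded and says information will be withheld from surgical providers, but a model and a pre-bent plate cannot be hidden from the person using them.
2. The interventions differ at the step of interest. If hand bending in theatre marked the boundary of the critical part, that step might be absent in the 3D arm, and the interval would then differ by definition.
3. Plastic surgery and otolaryngology also take part (3.1 and 10.1), yet 5.1 gives the judgement to OMS staff. Who judges the other services' cases is not stated.

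**The case against.** The list in 17.5 sits in a section on data handling and is clearly not complete. It omits the eligibility form in REDCap (10.1), the consent date (23.1) and even Outcome 1, the examination at about six weeks. Its time item is a short label that could cover both intervals. Field definitions normally sit in the case report form, which is not shown. There is also recording text that covers both arms: 6.5 sends outcome data to REDCap, 17.2 has the research coordinator enter data there, and 6.1 allows chart review without limit by arm. Section 5.1 does name who judges the critical part.

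Most of this stands, and it rules out two stronger readings. A reader might infer that the critical-part time is missing only in controls, because only surgeons in the 3D arm are surveyed. The documents do not support that: the survey asks for perceived saving, so neither arm has a stated source and no difference in missing data between arms can be read from the text. A reader might also infer that half of the hypothesis cannot be tested. That goes too far as well: both times are declared outcomes, and an undefined variable is not a variable that will not be measured. Nor does any section require both times to succeed; 5.1 lists them separately.

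What the objection does not supply is a start, an end, a source or a moment of recording for the critical part. The recording text is generic. It says where data go, not what is timed.

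**Conclusion.** The point holds in limited form. The protocol names two times to compare, lists one undefined time to collect, leaves blank the section that should describe collection, and leaves the critical part to judgement by staff who can know the arm. It does not secure an unbiased critical-part time in either arm, for any of the 100 planned procedures. The size of any bias cannot be calculated from the protocol.

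This rests on two assumptions: that no case report form outside the protocol already fixes the two events, and that the operating surgeon is aware of the model, which follows from the intervention itself. If such a form exists, what remains is to bring 5.1, 6.6 and 17.5 into line with it. If not, the correction should come before enrolment, since times not taken in theatre are lost.

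**What to change.** 1. In 17.5 and 6.6, replace the single procedural time with two items for all 100 procedures: total OR time (patient in room, patient out of room) and critical-part time (start, end). Give the source and the recorder for each.
2. In 5.1, fix the start and end of the critical part in advance as observable surgical steps. The surgeons should choose them. They must occur in every case, in both arms and in all participating services, so a step that pre-bending may remove cannot serve as a marker.
3. Enter the clock times during the case, not from memory and not through the 3D-arm questionnaire. Keep perceived time saved as a separate, subjective item.

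**Cost.** Four clock times replace one item, a net three fields if that item was a single field, or 4 × 100 = 400 short entries over the trial. Someone in theatre must note them. Section 3.2 describes a full-time research coordinator but does not say that this person attends operations, and 17.3 lets only the coordinator add data. The protocol should therefore say whether theatre staff note the times for the coordinator to enter, or are given entry rights.

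Fixed events do not blind anyone. They narrow the room for judgement that depends on the arm.
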